6.6. Concomitant Medications and Procedures

All concomitant medications and treatments (including over-the-counter or prescription medicines, vitamins, vaccines, and/or herbal supplements) must be recorded in the eCRF. Any prior medication received up to 28 days before the first dose of study treatment and 28 days after the last dose of study treatment will be recorded in the eCRF.

Any addition, deletion, or change in the dose of these medications will also be recorded. Concomitant treatments/procedures that are required to manage a participant's medical condition during the study will also be recorded in the eCRF. The medical monitor should be contacted if there are any questions regarding concomitant or prior therapy.

6.6.1. Prior Medications and Therapies

Prior and current medications and procedures will be reviewed to determine eligibility. All medications taken within 28 days before the first dose of study treatment will be recorded in the eCRF. A detailed history of prior medications use related to HS in the year before screening will be also be collected, as well as response to each treatment and reason for discontinuation.

6.6.2. Permitted Medications and Procedures

6.6.2.1. Antibiotic Therapy

After Week 4, if a participant experiences signs or symptoms indicative of an infection at an HS site (eg, fever and local/regional lymphadenopathy), the following antibiotic therapy may be initiated without interruption of study drug administration:

• Amoxicillin 500 mg/clavulanic acid 125 mg, 2 tablets, 3 times daily for 3 days

In participants for whom amoxicillin is contraindicated, the investigators should consult with the sponsor or designee to discuss alternative treatment options.

6.6.2.2. Analgesic Therapy

If a participant experiences significant pain after baseline, one of the following analgesic regimens may be initiated at any time:

- Ibuprofen (at a dose of up to 800 mg orally every 6 hours) not to exceed 3200 mg/24 hours.
- Acetaminophen not to exceed 4 g/24 hours.

If pain is not sufficiently controlled with one of the above regiments, a revised analgesic regiment can be considered in consultation with the sponsor or designee.

Dose adjustments in these analgesics on an as needed basis up to the maximum permitted dose and frequency are allowed during the study.

Analgesic usage (yes/no) will be recorded daily (see Appendix F).

6.6.2.3. Antiseptic Therapy

It is recommended that participants can use a daily antiseptic wash on their HS lesions. Permitted antiseptic washes are limited to one of the following: chlorhexidine gluconate, triclosan, benzoyl peroxide, or diluted bleach in bathwater.

6.6.2.4. Wound Care

Concomitant use of wound care dressings on HS wounds is allowed. Options are limited to alginates, hydrocolloids, and hydrogels.

6.6.3. Prohibited Medications and Procedures

The following medications are prohibited for all participants in the study:

- JAK inhibitors, systemic or topical (eg, ruxolitinib, tofacitinib, baricitinib, filgotinib, lestaurtinib, and pacritinib).
- Adalimumab or any other TNF- α treatment or any experimental treatments.
- Systemic immunosuppressive or immunomodulating drugs (eg, oral or injectable corticosteroids, methotrexate, cyclosporine, and azathioprine).
- Systemic and/or biologic therapies with potential therapeutic impact for HS.
- Surgical, laser, or IPL intervention in area with HS lesion, except as specified in Section 8.2.4 for rescue lesional treatment.
- Systemic anti-infectives (eg, antibiotics, antivirals, and antifungals), except as described in Section 6.6.2.1 for antibiotic therapy, or topical anti-infectives on HS lesions.
- Conventional therapies with potential therapeutic impact for HS.
- Topical antiseptic washes, creams, soaps, ointments, gels, and liquids containing antibacterial agents to treat HS, except those listed in Sections 6.6.2.3 and 6.6.2.4.

- Potent systemic CYP3A4 inhibitors or inducers or fluconazole.
 Note: Topical agents with limited systemic availability are permitted.
- Concomitant uses of P-gp inhibitors and inducers (see Appendix C) need to be consulted with the medical monitor.
- Live vaccines (during the study and within 6 weeks after EOT).

6.6.4. Rescue Lesional Treatments

Rescue lesional treatments are described in Section 8.2.4, as the need for rescue lesional treatment is considered an efficacy assessment.

7. DISCONTINUATION OF STUDY TREATMENT AND PARTICIPANT DISCONTINUATION/WITHDRAWAL

7.1. Discontinuation of Study Treatment

7.1.1. Reasons for Discontinuation

Participants **must** be withdrawn from study treatment for the following reasons:

- Consent is withdrawn.
 - Note: Consent withdrawn means that the participant can no longer be followed. Participants who choose to discontinue study treatment will be encouraged to remain in the study for safety monitoring.
- Further participation would be injurious to the participant's health or well-being, in the investigator's medical judgment.
- The study is terminated by the sponsor.
- The study is terminated by the local health authority, IRB, or IEC.

A participant **may** be discontinued from study treatment as follows:

- If, during the study, a participant is found not to have met eligibility criteria, the medical monitor, in collaboration with the investigator, will determine whether the participant should be discontinued from the study treatment.
- If a participant is noncompliant with study procedures or study drug administration in the investigator's opinion, the sponsor should be consulted for discussion regarding the participant's continued participation.

7.1.2. Discontinuation Procedures

In the event that the decision is made to permanently discontinue the study treatment, the EOT visit should be conducted. Reasonable efforts should be made to have the participant return for a follow-up visit. These visits are described in Table 3 and Section 8.7. The last date of the last dose of study drug and the reason for discontinuation of study treatment will be recorded in the eCRF.

If a participant is discontinued from study treatment:

- The study monitor or sponsor must be notified.
- The reason(s) for withdrawal must be documented in the participant's medical record and the primary reason for withdrawal must be included in the eCRF.
- The EOT visit should be performed.
- The date of the EOT visit should be recorded in the eCRF.
- Participants must be followed for safety until the time of the follow-up visit or until study drug—related toxicities resolve, return to baseline, or are deemed irreversible, whichever is longest.

If the participant discontinues study treatment and actively withdraws consent for collection of follow-up data (safety follow-up or disease assessment), then no additional data collection should occur; however, participants will have the option of withdrawing consent for study treatment but continuing in the follow-up period of the study for safety/efficacy assessments.

7.2. Participant Withdrawal From the Study

A participant may withdraw from the study at any time at his/her own request or may be withdrawn at any time at the discretion of the investigator for safety, behavioral, compliance, or administrative reasons.

If the participant withdraws consent for disclosure of future information, the sponsor may retain and continue to use any data collected before such a withdrawal of consent.

If a participant withdraws from the study, he/she may request destruction of any samples taken and not tested, and the investigator must document this in the site study records.

See Table 3 for data to be collected at the time of study discontinuation and follow-up and for any further evaluations that need to be completed.

7.3. Lost to Follow-Up

A participant will be considered lost to follow-up if he or she repeatedly fails to return for scheduled visits and is unable to be contacted by the study site.

The following actions must be taken if a participant fails to return to the clinic for a required study visit:

- The site must attempt to contact the participant and reschedule the missed visit as soon as possible. The participant will be counseled regarding the importance of maintaining the assigned visit schedule and ascertain whether or not the participant wishes to and/or should continue in the study.
- Before a participant is deemed lost to follow-up, the investigator or designee must make every effort to regain contact with the participant (where possible, 3 telephone calls and, if necessary, a certified letter to the participant's last known mailing address

- or local equivalent methods). These contact attempts should be documented in the participant's medical record.
- Should the participant continue to be unreachable, he/she will be considered to have withdrawn from the study with a primary reason of lost to follow-up.

8. STUDY ASSESSMENTS AND PROCEDURES

8.1. Administrative and General Procedures

8.1.1. Informed Consent Process

- The investigator or his/her representative will explain the nature of the study to the participant or his/her legally authorized representative and answer all questions regarding the study.
 - Informed consent must be obtained before any study-related procedures are conducted, unless otherwise specified by the Protocol.
 - Informed consent must be obtained using the IRB/IEC-approved version in a language that is native and understandable to the participant. A template will be provided by the sponsor or its designee. The sponsor or its designee must review and acknowledge the site-specific changes to the ICF template. The ICF must include a statement that the sponsor or its designee and regulatory authorities have direct access to participant records.
 - The ICF must contain all required elements and describe the nature, scope, and possible consequences of the study in a form understandable to the study participant.
- Participants must be informed that their participation is voluntary. Participants or their legally authorized representative will be required to sign a statement of informed consent that meets the applicable requirements and regulations for the country in which the study is being conducted as well as the IRB/IEC or study center.
- The participant must be informed that his/her personal study-related data will be used by the sponsor in accordance with local data protection laws. The level of disclosure must also be explained to the participant.
- The participant must be informed that his/her medical records may be examined by Clinical Quality Assurance auditors or other authorized personnel appointed by the sponsor, by appropriate IRB/IEC members, and by inspectors from regulatory authorities.
- The medical record must include a statement that written informed consent was obtained before the participant was enrolled in the study and the date the written consent was obtained. The authorized person obtaining the informed consent must also sign the ICF.

- Participants must provide consent to the most current version of the ICF(s) during their participation in the study.
- A copy of the ICF(s) must be provided to the participant or the participant's legally authorized representative.
- Participants who are rescreened are required to sign a new ICF.

8.1.2. Screening Procedures

Each participant will be identified in the study by a participant ID number, which is a combination of the site ID and participant number.

Screening is the interval between obtaining informed consent and the day of the first administration of study drug (Day 1). Screening assessments for determination of eligibility may be performed over a period lasting up to 28 days.

Procedures conducted as part of the participant's routine clinical management (eg, clinical laboratory tests) and collected before informed consent is obtained may be used for screening or baseline purposes, provided the procedure meets the protocol-defined criteria and has been performed within 28 days before Day 1. All information associated with eligibility requirements, including demography and medical history, must be entered into the appropriate eCRF pages.

Results from the screening assessments will be reviewed to confirm eligibility before administration of study drug. Tests results that do not meet eligibility requirements may be repeated once during screening if the investigator believes there is a reasonable possibility that the participant would be eligible if retested. For screening assessments that are repeated, the most recent available result before administration of study drug will be used to determine eligibility. See Section 5.4 regarding screen failures.

8.1.3. Distribution of Reminder Cards and Diaries

Participants will be provided with a reminder card at the visits indicated at Table 3. The reminder card will indicate the date/time of the next visit and will also remind the participant that they should not take study drug on Day 1, Week 4, and Week 8 visits, as they will take it after blood draws for safety evaluation have been completed. The reminder cards will have an area on which the date and time of the last dose taken (from the previous evening) for Week 4 and Week 8 visits and the time of their last meal before the visit for Day 1, Week 2, Week 4, Week 6, and Week 8 will be recorded.

Diaries will be provided to participants at the visits indicated at Table 3 to record HS pain NRS (see Section 8.2.5) and analgesic use (see Section 8.2.6).

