6. STUDY TREATMENT

6.1. Study Treatment Administered

Information regarding study drug and administration is provided in Table 6. Participants will record study drug administration in a daily diary. Participants will take the study drug once daily, preferably in the morning.

Table 6: Study Treatment Information

Study treatment name:	INCB054707
Dosage formulation:	Tablet
Unit dose strength/dosage level:	INCB054707 15 mg QD
Route of administration:	Oral
Administration instructions:	INCB054707 will be taken orally with water without regard to food.
Packaging and labeling:	INCB054707 will be provided as 15 mg tablets and labeled as required per country requirement.
Storage:	Ambient (15°C-30°C/59°F-86°F)

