8.3.4. Electrocardiograms

All 12-lead ECGs will be performed with the participant in a recumbent or semirecumbent position after at least 5 minutes of rest.

Electrocardiograms should be performed as indicated in Table 3. Additional 12-lead ECGs may be performed at other visits as deemed clinically necessary. Electrocardiograms will be interpreted by the investigator at the site, and the results will be used for immediate management of the participant's care. The decision to include or exclude a participant or withdraw a participant from the study based on an ECG flagged as "Abnormal, Clinically Significant" is the responsibility of the investigator, in consultation with the sponsor's medical monitor, as

appropriate. Any abnormalities that are considered clinically significant in the judgment of the investigator are to be reported as AEs.

Table 9: Electrocardiogram Schedule

	Timing of ECG Relative to Administration of Study Drug						
Study Visit	Not Applicable	Predose (trough) ECG ^a	Postdose ECG ^b				
Screening	Single → Triple						
Day 1		Triple ^c	Single → Triple				
Week 2			Single → Triple				
Week 6			Single → Triple				
Week 8 (EOT)		Single → Triple					

^a Predose ECG should be performed 5 to 10 minutes before the predose PK assessment.

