9.9. Treatment of Overdose

For this study, any dose of INCB054707 greater than 15 mg within a 24-hour time period will be considered an overdose. Sponsor does not recommend specific treatment for an overdose.

In the event of an overdose, the investigator should:

- Contact the medical monitor immediately.
- Closely monitor the participant for any AE/SAE and laboratory abnormalities until INCB054707 can no longer be detected systemically (at least 3 days).
- Obtain a plasma sample for PK analysis within 3 days from the date of the last dose of study treatment if requested by the medical monitor (determined on a case-by-case basis).
- Document the quantity of the excess dose as well as the duration of the overdose in the eCRF.

Decisions regarding dose interruptions or modifications will be made by the investigator in consultation with the medical monitor based on the clinical evaluation of the participant.

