8.5. Electrocardiograms

All 12-lead ECGs will be performed as indicated in Table 5 with the participant in a recumbent or semirecumbent position after at least 5 minutes of rest. Additional 12-lead ECGs may be performed at other visits as deemed clinically necessary. Electrocardiograms will be interpreted by the investigator at the site, and the results will be used for immediate management of the participant's care. The decision to include or exclude a participant or withdraw a participant from the study based on an ECG flagged as "Abnormal, Clinically Significant" is the responsibility of the investigator, in consultation with the sponsor's medical monitor, as appropriate. Any abnormalities that are considered clinically significant in the judgment of the investigator are to be reported as AEs.

Descriptive statistics and mean change from baseline will be determined for each ECG parameter at each assessment time. Change and percentage change from baseline will be calculated. Triple ECGs will be measured at baseline and postbaseline visits if necessary. Electrocardiogram abnormalities, both at baseline and postbaseline visits, will be tabulated. Incidences of abnormalities will be listed with study visit and a description of the abnormality.

Table 5: Electrocardiogram Schedule

	Timing of ECG Relative to Administration of Study Drug		
Study Visit	Not Applicable	Predose (trough) ECG ^a	Postdose ECG ^D
Screening	Single → Triple		
Day 1		Triple ^c	Single → Triple
Week 2			Single → Triple
Week 6			Single → Triple
Week 8 (EOT)		Single → Triple	

Note: Single → Triple: Single ECG will be performed first. If abnormal ECG results are observed, an additional 2 ECGs will be measured within the next 5 minutes.

^a Predose ECG should be performed 5 to 10 minutes before the predose PK assessment.

b Postdose ECGs will be performed when participants arrive at the study sites

If abnormality ECG results are observed, an additional 2 ECGs will be measured within the next 5 minutes. Postdose ECG will be measured

^c Day 1 predose 12-lead ECGs will be performed in triplicate, and values will be averaged to calculate the baseline values.

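### Holding the Week 4 and Week 8 dose for the clinic turns a previous-evening dose into a protocol-defined overdose, and makes the Week 8 predose ECG something other than a trough

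*Protocol*

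**What the plan says.** Four places in the plan bear on when the daily dose is taken.

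- **Protocol 6.1.** "Participants will take the study drug once daily, preferably in the morning". Morning is a preference; evening dosing is not ruled out. Table 6 adds that "INCB054707 will be provided as 15 mg tablets", so one tablet is the whole daily dose.
- **Protocol 8.1.3.** The reminder card tells participants that "they should not take study drug on Day 1, Week 4, and Week 8 visits, as they will take it after blood draws". The same card has a space to record "the date and time of the last dose taken (from the previous evening) for Week 4 and Week 8 visits".
- **Protocol 9.9.** "any dose of INCB054707 greater than 15 mg within a 24-hour time period will be considered an overdose". The investigator's first step is "Contact the medical monitor immediately". Close monitoring for at least 3 days, a plasma sample if the medical monitor asks for one, and eCRF documentation follow. Doses given at a visit are not exempted.
- **Protocol 8.3.4 (Table 9) and SAP 8.5 (Table 5).** The Week 8 ECG sits in the column headed "Predose (trough) ECG". SAP 8.5 summarises each ECG parameter by assessment time and states no rule that uses hours since the last dose.

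**The concern.** The card's wording fits someone who takes the drug in the evening. Section 6.1 expects most people to take it in the morning, and for them the last dose before a Week 4 or Week 8 visit would be the previous morning. The text supplied does not reconcile the two.

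Two things are at stake. First, an evening doser who does what the card says at the visit takes a second tablet well inside 24 hours. That sets off the overdose steps although nobody has departed from the instructions. Second, ECGs belong to the primary safety endpoint. If the Week 8 predose ECG is taken midway between doses in some participants and at the end of the interval in others, a single Week 8 summary labelled as a trough mixes two different exposures.

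**Working it through.** The plan has no sample-size or error-rate figure on this point. The only stated figure is the overdose threshold, more than 15 mg within 24 hours.

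**Inputs from the documents:** tablet 15 mg (6.1); dose held at home and taken in clinic at Weeks 4 and 8 (8.1.3); threshold 15 mg in 24 hours (9.9); enrolment of up to 10 (4.1).

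**Assumed inputs:** the documents give no clock times. I take evening doses at 18:00 to 22:00 and clinic doses at 08:00 to 12:00, with some previous-morning doses for comparison.

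**Step 1: gap and dose within 24 hours.** Gap = clinic time + 24 h − time of the previous day's dose. If the gap is under 24 h, the amount is 2 × 15 = 30 mg; otherwise it is 15 mg.

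| Last dose, previous day | Clinic dose | Gap (h) | mg within 24 h | Above 15 mg? |
|---|---|---|---|---|
| 22:00 | 08:00 | 8 + 24 − 22 = 10 | 30 | yes |
| 22:00 | 09:00 | 9 + 24 − 22 = 11 | 30 | yes |
| 20:00 | 09:00 | 9 + 24 − 20 = 13 | 30 | yes |
| 18:00 | 09:00 | 9 + 24 − 18 = 15 | 30 | yes |
| 18:00 | 12:00 | 12 + 24 − 18 = 18 | 30 | yes |
| 08:00 | 09:00 | 9 + 24 − 8 = 25 | 15 | no |
| 07:00 | 09:00 | 9 + 24 − 7 = 26 | 15 | no |
| 10:00 | 09:00 | 9 + 24 − 10 = 23 | 30 | yes |

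Every evening row exceeds the threshold, so the result does not hang on one chosen time. The last row shows that, read literally, the definition also catches a morning doser whose clinic dose comes slightly earlier than the dose of the day before.

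**Step 2: how many.** Each evening doser has at most two such clinic doses, at Weeks 4 and 8. With k evening dosers the ceiling is 2k. The documents give no value for k.

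**Step 3: which scheduled ECGs.** Going through Table 9:

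- Day 1 predose: no earlier dose, so unaffected.
- Week 4: no ECG scheduled.
- Weeks 2 and 6: postdose only (see the objection).
- Week 8: predose, labelled as trough, so affected.

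The Week 8 ECG is taken shortly before the clinic dose, so its time since dose is close to the gap in Step 1: about 10 to 18 h for an evening doser, against about 24 h or more for a morning doser (25 to 26 h in the 07:00 and 08:00 rows).

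**The case against.** The best defence is that the card records a dose time and does not prescribe one. The only instruction on time of day is in Section 6.1, and it prefers the morning. A participant who follows that preference and has at least 24 hours between doses never meets the overdose definition. The mention of the previous evening may be no more than a drafting slip. This is correct as far as it goes, and it rules out reading the card as an order to dose in the evening. It does not remove the conflict, because evening dosing is permitted, the card expects it, and Section 9.9 makes no allowance for it.

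A reader might infer more than the documents support:

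- **Twenty overdoses.** 10 × 2 = 20 is reached only if all ten participants dose in the evening before both visits. Nothing in the documents says how many will.
- **Trough ECGs wrong at both visits.** Week 4 has no scheduled ECG. Among scheduled ECGs, only Week 8 is exposed.
- **PK samples and postdose ECGs mistimed.** The footnote says "Postdose ECGs will be performed when participants arrive at the study sites", which suggests a dose taken at home beforehand, but the rest of that footnote and the PK sampling section are missing from the text supplied. A timing window may be stated there, so the point cannot be judged either way.
- **Inflated adverse event counts.** Under Protocol 9.1, an overdose is reportable as an adverse event in itself only if intentional with possible self-harming intent. The burden here is contact, monitoring and documentation.

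It is also fair to say that the ECG summaries are descriptive and that SAP 3.2 calls all analyses exploratory. No hypothesis test is affected.

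**Conclusion.** The inconsistency is real but narrow. Anyone who took the previous dose in the evening and then takes the Week 4 or Week 8 dose in clinic has 30 mg within about 10 to 18 hours, twice the 15 mg limit in Section 9.9, and so triggers the overdose procedures by complying. A morning doser with a gap of 24 hours or more does not. The number affected is unknown, with a ceiling of two clinic doses per evening doser.

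For the same people, the Week 8 predose ECG falls about 10 to 18 hours after dosing and is not a trough, and the SAP as written would not show which ECGs these are.

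The hours rest on the assumed clock times. The overdose result rests on reading the 24-hour limit as cumulative, which is its natural sense. Nothing is concluded about PK sampling or the postdose ECGs.

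**What to change.** **Protocol.** Sections 6.1, 8.1.3 and 9.9 and Table 9 (with SAP Table 5) must be reconciled to one consistent dosing clock. The reconciled text should state how the in-clinic dose at Weeks 4 and 8 relates to the overdose definition. Which time of day applies, and how the definition should read, is for the sponsor to settle; none is proposed here.

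**SAP.** List the recorded hours since last dose beside the Week 8 predose ECG, for example as a column in the planned listing of 12-lead ECG values, so that ECGs that are not true troughs can be identified. The reminder card already asks for the last-dose date and time at Week 8. The documents do not say that the entry is carried into the database, so that should be confirmed.

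I would not reclassify every ECG as predose or postdose by elapsed hours. That needs a cut-off that the plan does not give. It also needs dose times at Weeks 2 and 6, where the card asks only for the last meal and Section 6.1 does not say whether the dosing diary records clock time.

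**Cost.** Wording changes in an amendment and on the reminder card, plus one derived variable in one listing.
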